### **4.0 STUDY DESIGN**

This study is a prospective, multicenter, bilateral, non-randomized, open-label, comparative clinical study conducted at up to 80 sites in the USA. Subjects will choose to be bilaterally implanted with either 1) the TECNIS 1-Piece Toric IOLs, Model ZCT300 and/or ZCT400, or 2) the TECNIS Monofocal Model ZCB00 non-toric control IOL, according to subject preference.

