## 20.2 PRIMARY ENDPOINT ANALYSIS

The primary endpoint is the rate of severe visual distortions (under overall circumstances) as measured by the 5 defined visual distortion items at 6 months postoperative. The frequency and proportion of bilateral subjects with severe visual distortions will be presented for toric IOL and control IOL subjects. Any subject with missing data for visual distortion symptoms at the 6-month visit will have the last reported value carried forward, if the subject had an earlier visit. Results for severe visual distortions will be evaluated using a non-inferiority approach with a non-inferiority margin of 10%. The upper limit of the 90% confidence interval of the difference in severe visual distortion rates (toric minus control) will be used to evaluate this endpoint.

The null hypothesis,  $H_0$ , is:  $p_{\text{Toric}} - p_{\text{Control}} \geq 0.10$

The alternate hypothesis,  $H_1$ , is:  $p_{\text{Toric}} - p_{\text{Control}} < 0.10$

With  $p$ =proportion reporting severe visual distortions

A logistic regression analysis for severe visual distortions will be performed with age, sex, race, and cylinder subgroup as well as age by IOL group and sex by IOL group as covariates to evaluate the influence of these variables.

To evaluate if toric IOL axis misalignment relative to keratometry are associated with severe visual distortions, descriptive statistics for IOL axis misalignment will be reported for toric subjects with and without severe visual distortions. In this study, axis misalignment is defined as the difference between the toric IOL axis marker location from the slit-lamp evaluation and the steep meridian from the postoperative keratometry measurement. This measurement is intended to evaluate toric IOL misalignment as a possible reason for severe visual distortions experienced by a subject at a specific postoperative time point. This axis misalignment measurement is not a measure of toric IOL rotational stability, but a measure of toric IOL alignment relative to post-surgical keratometry steep meridian, as it is known that cataract surgery can induce changes in the cornea.

The frequency and proportion for the rate of severe visual distortions will also be presented for those in the low- and high-cylinder subgroups for toric and control subjects.

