## 20.6 SAMPLE SIZE

A sample size of a minimum of 396 enrolled subjects to achieve bilateral implantation of approximately 294 subjects: 169 TECNIS Toric ZCT300 and ZCT400 and 125 control subjects is reflective of the number of subjects enrolled on the date of this protocol revision (3.0).

A two-group large-sample normal approximately test of proportions with a one-sided 0.05 significance level using only 37 evaluable toric subjects and 27 evaluable control subjects will have a greater than 90% power to detect a rate of severe visual distortions for toric subjects as being 10 percentage points or greater than that for control subjects. This assumes severe visual distortion rates of 1% for both the toric and control subjects. Therefore, the sample size proposed for a minimum of 396 enrolled subjects, assuming a 10% drop out rate for a minimum of 152 toric and 112 control subjects available for evaluation at 6 months, is sufficient to demonstrate non-inferiority in the rate of severe visual distortions (the primary endpoint of this study) between the two study groups in a larger population in clinical practice and thereby demonstrate the continued safety of the toric IOLs.

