2.3 Randomization

Subjects will not be randomized in this study.

3. Accountability/Demographics

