4.2 Other Visual Distortion Endpoints Related to Severe Visual Distortions

In addition to the above information related to the primary endpoint analysis, other analyses will also be performed for severe visual distortion rates (based on the 5 defined items) and will include the frequency and proportion with severe visual distortions. Severe visual distortion data for the overall circumstance will be reported for the low (ZCT300) and high cylinder (ZCT400) subgroups for bilateral subjects to evaluate if there is a trend of increasing severity for the higher cylinder IOL group. The severe visual distortion rate will also be reported by IOL group for all subjects (bilateral plus those implanted in one eye (with a cataract, phakic or having another IOL in the fellow eye). In addition, an analysis including all subjects using imputed data for subjects with no questionnaire data available at any visit will also be reported.

Additional analyses including covariates will also be performed for bilateral subjects. A logistic regression model with overall severe visual distortion rates as the dependent variable and IOL group, age, gender, race, cylinder power (low- vs high-cylinder subgroups) and the interaction of age with IOL group and gender with IOL group as independent variables will be performed to further evaluate the influence of these variables on severe visual distortions. If covariates are shown to be important then additional analyses will be provided for those covariates. Results for severe visual

distortions will also be reported by study site for each IOL group. Although there are a large number of sites, any unusual patterns will be noted (i.e. all severe visual distortions at 1 or 2 sites) and further analyses performed to address any site issues.

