With 200 toric (ZCT) subjects and 150 control (ZCB00) subjects, this study has over 90% power to evaluate the rate of severe visual distortions for toric subjects as being no more than 10 percent higher than control subjects. This assumes use of one side of a two-sided 90% confidence interval and severe visual distortion rates of 0.02 for toric and control subjects.

With approximately 70 subjects in the higher cylinder toric subgroup (those with a ZCT400 IOL in one or both eyes) the precision of the one-sided upper confidence limit for the proportion of those with severe visual distortions is approximately 0.05 to 0.06 assuming a rate for severe visual distortions of 0.02.

REFERENCES

- 1. Little, R.and Rubin, D. Statistical Analysis with Missing Data, John Wiley & Sons, Inc. New York, Second Edition, (2002)
- 2. SAS Institute. The MI and MIanalyze Procedures. SAS/STAT 9.2 User Guide. Cary, N.C.

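### On the plan's own event rates, the only covariate model (with sex-by-lens) usually has no finite fit, and preoperative distortion ratings are not compared between self-selected lens groups

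*SAP*

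**What the plan says.** - **Allocation.** Protocol 4.0 has the lens chosen "according to subject preference". SAP 2.3 confirms: "Subjects will not be randomized in this study".
- **Primary analysis.** Protocol 20.2 and SAP 4.1 compare the upper limit of a two-sided 90% interval for the unadjusted difference (toric minus control) with 0.10. Neither names the interval method.
- **Covariate model.** SAP 4.2 specifies a logistic regression for bilateral subjects on "IOL group, age, gender, race, cylinder power (low- vs high-cylinder subgroups) and the interaction of age with IOL group and gender with IOL group", in order "to further evaluate the influence of these variables on severe visual distortions". It then adds: "If covariates are shown to be important then additional analyses will be provided for those covariates". Protocol 20.2 has the same model: "A logistic regression analysis for severe visual distortions will be performed with age, sex, race, and cylinder subgroup", plus age by lens group and sex by lens group. Neither document names an estimator other than ordinary logistic regression, or a rule for sparse events or non-convergence.
- **Planning rates.** Protocol 20.6, with 152 toric and 112 control subjects evaluable: "This assumes severe visual distortion rates of 1% for both the toric and control subjects". SAP section 7, with 200 and 150 subjects, assumes "severe visual distortion rates of 0.02 for toric and control subjects".
- **Preoperative PRVDQ.** Protocol 11.3 and Appendix A give the questionnaire to every subject before surgery. SAP 3.3 summarises demographics, iris colour and operative events, but not these ratings. Protocol 20.3 and SAP 4.3 report item responses by lens group without naming a visit. However, Protocol 6.0 sets endpoints at 6 months, and SAP Appendix I lists the questionnaire rows under postoperative data. SAP 4.4 mentions questionnaire responses only as possible detail for subjects with events.

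**The concern.** In a self-selected, open-label comparison, this regression is the only named analysis that looks at lens group with other variables held fixed. It has many terms and the plan expects very few events. If the fit has infinite coefficients, the Wald tests attached to them mean nothing, and a rule that acts on important covariates has little to act on. With no fallback written down, a replacement would be chosen after the data are seen.

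The missing baseline summary is a separate gap. Without it, a reader of the report cannot tell whether the two groups already differed in distortions before surgery.

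**Working it through.** **Inputs.** 152 and 112 evaluable at 1% (Protocol 20.6); 169 and 125 implanted (same section); 200 and 150 at 2% (SAP section 7). The documents give no sex, race or age mix, so those are assumptions.

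**The plan's own figure.** Protocol 20.6 states more than 90% power with 37 and 27 subjects at 1%, one-sided 0.05. The normal approximation gives Φ(0.10/√[0.01 × 0.99 × (1/37 + 1/27)] − 1.645) = Φ(3.97 − 1.645) = 0.990. The statement is reproduced.

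**Parameters.** Intercept, lens, age, sex, race, cylinder, age-by-lens, sex-by-lens: 8 if age is linear and race has two classes, more otherwise.

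**Expected events.** 264 × 0.01 = 2.64; 350 × 0.02 = 7.0. The chance of fewer than 4 events is 0.728 at 264 and 1%, and 0.080 at 350 and 2%.

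**Exact floor.** With lens, sex and their product in the model, each of the four lens-by-sex cells has its own free level. If a cell has no events, the likelihood keeps rising as that level goes to minus infinity, so no finite maximum exists. The chance that all four cells have an event is greatest at an even sex split. Taking one rate for all cells:

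- 152/112, 1%: (1 − 0.99^76)² × (1 − 0.99^56)² = 0.534² × 0.430² = 0.053. No finite fit in at least 94.7%.
- 169/125, 1%: 0.071. At least 92.9%.
- 200/150, 2%: (1 − 0.98^100)² × (1 − 0.98^75)² = 0.867² × 0.780² = 0.458. At least 54.2%.

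Age, race and cylinder can only raise these. At a 65/35 sex split the floors for 152/112 and 200/150 become 95.6% and 60.5%. At 152/112 with a 2% rate the floor is 71.7%.

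**Simulation.** A linear-programming test for separation was run with equal rates, age N(70, 8.5), and an assumed 55% female, 15% minority race and 30% high cylinder (1,000 trials per setting for the first four rows, 300 for the last two).

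| Result | 152/112, 1% | 200/150, 2% |
|---|---|---|
| Some coefficient not finite | 97.2% | 69.3% |
| Lens contrast (age 70, averaged over sex) not finite | 95.1% | 54.0% |
| Interactions dropped: some coefficient not finite | 87.8% | 47.3% |
| Interactions dropped: lens coefficient not finite | 49.8% | 6.6% |
| Age coefficient finite | 69% | 93% |
| At least one covariate main effect finite | 77% | 97% |

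At 152/112 and 1%, cylinder is finite in 40%, race in 28% and sex in 19%. Over two other assumed mixes the first row was 95.0% and 99.7% (59.0% and 86.0% on SAP inputs).

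**Groups with no events.** 0.99^152 + 0.99^112 − 0.99^264 = 0.217 + 0.324 − 0.070 = 0.471. This explains most of the 49.8%, and no estimator can supply the missing information.

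**Effect on the primary decision.** At 1%, 152 × 0.01 = 1.5 toric events are expected. Wald upper limits with 11 toric events are 7.24 + 1.645 × 2.10 = 10.7 points (0 control events) and 6.34 + 1.645 × 2.28 = 10.1 points (1 control event). With 10 toric and 0 control events the Wald limit is 6.58 + 1.645 × 2.01 = 9.9 points, but the Newcombe limit is 10.7. So with 0 or 1 control events the test fails only from about 10 or 11 toric events, depending on the method.

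**Replacement.** One-at-a-time Firth models at 152/112 and 1% gave finite fits in 232 of 233 trials (lens plus age), 233 of 233 (sex) and 233 of 233 (race). Lens plus cylinder was not run alone. A Firth model of lens, preoperative score and cylinder was finite in all 1,491 trials with events. Over the assumed score distributions, its median 90% limits for the lens odds ratio were 0.09–0.18 to 6.2–7.2.

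**The case against.** The strongest reply is that a fit with some infinite coefficients is not an empty fit. That stands. Age is finite in about 69% of trials on protocol inputs, and some covariate main effect in about 77%. The failure is concentrated in sex, sex-by-lens and the lens contrast. But what remains rests on about three events, which is little basis for calling a covariate important.

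Second, the model is supportive and its stated purpose is to explore covariate influence, not to adjust for confounding. That also stands, so the remedy should keep the plan's own covariates. A preoperative rating, taken with cataracts in place, should not become the centre of the model; the documents do not show that it predicts 6-month distortions.

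Third, the plan already reports rates by cylinder subgroup and by site, and allows detailed review of subjects with events. This helps, but it gives neither an adjusted lens estimate nor a baseline comparison that includes subjects without events.

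Fourth, preoperative astigmatism is largely handled by design: both groups must qualify on the toric calculator, and controls are classed by the lens they would have needed (Protocol 8.2, 11.3 and 20.1). No claim is made there.

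**Conclusion.** The point holds and is minor. As written, the full model has no finite maximum-likelihood fit in at least 94.7% of trials on Protocol 3.0 inputs and at least 54.2% on the 2015 SAP inputs. Those floors assume the stated sample sizes and one event rate throughout; they need no assumption on the covariate mix. The figures for single coefficients and for the lens contrast do depend on an assumed mix. The missing preoperative PRVDQ summary follows from the text alone.

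A reader might infer three stronger things that the documents do not support:

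- That the non-inferiority conclusion is unsafe. The primary test does not use this model, and failure would need about 10 or 11 toric events when about 1.5 are expected.
- That the model would yield nothing at all. Some coefficients usually remain finite, though poorly determined.
- That the groups did differ in distortions before surgery. Nothing shows this; the plan simply would not reveal it. In illustrative runs with no true lens effect and an odds ratio of 2 per rating step, assumed imbalances gave mean unadjusted lens log odds ratios of −0.74 and −0.22. At a 1% rate these are roughly 0.7 and 0.2 points, against a 10-point margin.

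**What to change.** 1. In SAP 4.2 and Protocol 20.2, fit the supportive analysis by Firth-penalised logistic regression without the two interactions. Use one-at-a-time models: lens plus each of age, sex, race and cylinder subgroup. Report 90% profile penalised-likelihood intervals, labelled supportive.
2. Write the sparse-event rule. With no events, report counts only. If one lens group has none (47% of trials at 1%), say that the interval mainly reflects the penalty.
3. In place of the interactions, give counts and rates by lens group within the SAP 3.3 age classes, sex and race.
4. Add the preoperative PRVDQ overall ratings for the five items, by lens group, to the SAP 3.3 baseline table and Appendix I. A Firth model of lens plus worst preoperative rating is optional.

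The cost is wording and programming; no new data are needed. Interactions and joint effects are no longer modelled, estimates are shrunk and intervals are wide, so evidence on confounding stays limited. Protocol 13.0 requires FDA and IRB approval for modifications. The change must be documented as made after the interim analysis recorded in the Change History for version 3.0.

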If correction is required during the study postoperatively, spectacles or contact lenses will be prescribed; however, no additional refractive procedures (LRI, AK, etc.) are allowed until after completion of the 6-month study visit. This is particularly important for non-toric control subjects who will likely have residual refractive cylinder for which they may need to wear correction until completion of the 6-month study exam. If a subject is required to return for a 1-year exam (due to a severe visual distortion at 6 months or an IOL repositioning procedure during the study), a refractive enhancement (LRI, AK, etc.) may be performed prior to the 1-year exam but must be reported on the 1-year CRF.

The postoperative case report form will collect the following information (Appendix A):

- ❖ Confirmation of offering of spectacle and/or contact lens prescription: 1-month visit only
- ❖ Questionnaire (Appendix B): 6-month and 1-year visits; also at 1-month or unscheduled visits only if there is a spontaneous report of visual distortion or prior to an IOL repositioning procedure at that visit.
- ❖ Keratometry, for toric IOLs only: 6-month and 1-year visits; also at 1-month and unscheduled visits if there is a spontaneous report of visual distortion or prior to an IOL repositioning procedure at that visit.
- ❖ Toric IOL axis measurement by dilated slit-lamp examination ,for toric IOLs only (Refer to Appendix C for measurement instructions): 6-month and 1-year visits; also at 1-month and unscheduled visits if there is a spontaneous report of visual distortion or prior to an IOL repositioning procedure at that visit.
- ❖ Medical and lens findings from biomicroscopic slit-lamp exam: 6-month and 1-year visits and may be performed at the 1-month and/or unscheduled visits if an ocular adverse event occurred at such visit or if a severe visual distortion is noted. Findings of aqueous cells and flare, corneal edema, posterior capsule striae, posterior capsular opacification and IOL glistenings are to be rated using the standardized grading scales provided in Appendix D.
- ❖ Ocular medications

- ❖ Dilated fundus exam, if medically indicated
- ❖ Occurrence of Nd:YAG capsulotomy(ies)
- ❖ Occurrence of any adverse events
- ❖ If an ocular adverse event or a severe visual distortion is noted at any postoperative study visit, the following additional information should be collected:
  - Monocular uncorrected distance visual acuity (Snellen)

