To evaluate if IOL axis misalignment changes are associated with severe visual distortions, descriptive statistics for IOL axis misalignment will be reported for Toric subjects with and without severe visual distortions. In this study, axis misalignment is defined as the difference between the Toric IOL axis marker location from the slit lamp evaluation and the steep meridian from the postoperative keratometry measurement. This measurement is intended to evaluate toric IOL misalignment as a possible reason for severe visual distortions experienced by a subject at a specific postoperative timepoint. This axis misalignment measurement is not a measure of toric IOL rotational stability, but a measure of toric IOL alignment relative to post-surgical keratometry steep meridian [as it is known that cataract surgery can induce changes in the cornea].

4.3 Other Visual Distortion Endpoints:

The frequency and proportion with each response will also be reported for individual visual distortion items on the questionnaire and will be reported by IOL group for bilateral subjects for overall and with and without correction.

4.4 Other Safety Endpoints:

The frequency and proportion of medical and lens findings will also be reported for first and second eyes of toric (ZCT) and control (ZCB00) subjects. The frequency and proportion of adverse events at any time postoperative will also be reported.

For subjects with serious or device related adverse events or reports of severe visual distortions, additional detailed information will be provided as appropriate and may include such items as uncorrected and corrected distance visual acuity, manifest refraction, keratometry, intraocular pressure, slit-lamp and dilated fundus exam findings, ocular medications, questionnaire responses and prognosis and treatment.

5. One Month Prescription Data:

The frequency and proportion of responses to the question related to offering of spectacle or contact prescription will be reported by IOL group at the one month visit.

6. One Year Data:

Visual distortion findings, adverse events and medical/lens findings at one year will be reported for subjects who experienced a repositioning procedure during the study and for subjects who were reported with severe visual distortions at the 6-month visit.

7. Sample Size Calculations

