APPENDIX I

TABLE LISTING

	First	First	Second	Second			
	Eyes	Eyes	Eyes	Eyes	Toric	Control	Comments
	Toric	Control	Toric	Control	ZCT	ZCB00	
	ZCT	ZCB00	ZCT	ZCB00	Subjects	Subjects	
ENROLLMENT/PREOP/OP							
Accountability/Enrollment							0 " "
No. of implants by IOL	X	X	Х	Х			Overall and by
model by investigational site							low/high
Site							cylinder
Accountability					V	V	subgroup
Accountability					Х	Х	
Demographics							
Demographic–Age in years					х	x	
(N, Mean, SD, Min., Max),					^	^	
age in groups (<60,60-							
69,70-79,>=80), race,							
ethnicity, gender, iris color							
gerraer, me sere							
Operative Data							
Surgical Complications: No.	Х	Х	Х	Х			
and percent with each							
response							
Surgical Other Procedures	Х	х	х	х			
(No. and percent with each							
response)							
POSTOPERATIVE DATA							
Time frame for Reporting:							
6 Months							
Prescription Offerred at One Month Visit					Х	Х	
One Wonth Visit							
Overall Severe Visual					x	x	Bilateral
Distortions					^	^	subjects
No.,percent and 90%Cl for							Subjects
those with and without							
severe visual distortions at 6							
Months or if missing 6 month							
data at an earlier visit							
Other Severe Visual							
Distortion Analyses							
Overall Severe Visual					Х	х	All subjects and
Distortions							by cylinder
(No, percent)							subgroup
Overall Severe Visual					x	x	Bilateral
Distortions By Site							subjects
(No. and percent)							

Other Visual Distortion	First Eyes Toric ZCT	First Eyes Control ZCB00	Second Eyes Toric ZCT	Second Eyes Control ZCB00	Toric ZCT Subjects	Control ZCB00 Subjects	Comments
Endpoints Individual Visual Distortions-Overall and With and Without Correction No, percent with each response for each item					X	X	Bilateral subjects
Axis Misalignment analysis and Severe Visual Distortion Difference between IOL axis marker location and steep K meridian (N, Mean, SD, Min. Max)					х		Bilateral subjects
Medical, Lens Findings							
No. and Percent with findings at 6 months	х	х	х	х			
Adverse Events							
No. and Percent with adverse events at any time postoperative	Х	х	х	х	х	х

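### Does the axis-misalignment table need a tighter definition and an added graded analysis?

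*SAP*

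**What the plan says.** SAP section 4.2 and Protocol section 20.2 state the same aim, to see whether misalignment of the toric lens is associated with severe distortion. The planned output is also the same; the SAP's wording is "descriptive statistics for IOL axis misalignment will be reported for Toric subjects with and without severe visual distortions". The angle to be summarised is "the difference between the Toric IOL axis marker location from the slit lamp evaluation and the steep meridian from the postoperative keratometry measurement". Both documents add that this reflects alignment at a given postoperative time and does not measure rotational stability.

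SAP Appendix I lists the row as N, mean, SD, minimum and maximum for bilateral toric subjects, within the block whose reporting time frame is 6 months. Only the toric-subject column is marked; the first-eye and second-eye columns are not.

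Protocol section 11.5 schedules keratometry and the axis reading at 6 months and 1 year for toric eyes, and "also at 1-month and unscheduled visits if there is a spontaneous report of visual distortion or prior to an IOL repositioning procedure". Protocol Appendix C has the axis recorded for each eye, while the questionnaire in Appendix B takes one answer for both eyes together.

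Under SAP section 2.1, a missing 6-month answer is replaced by the last earlier one. After a repositioning or removal, the last answer before the procedure is used. SAP section 4.4 adds case detail: "For subjects with serious or device related adverse events or reports of severe visual distortions, additional detailed information will be provided as appropriate".

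**The concern.** Protocol section 2.0 names axis misalignment as the possible source of spatial distortion with higher-cylinder toric lenses, so this is the table a reader would turn to for the mechanism.

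Two things look wrong:

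- **Definition.** The measure is open on sign and on folding at 180 degrees, on how two eye values become one subject value, and on which axis reading goes with a carried-forward or pre-repositioning answer. Two analysts could print different means, SDs and maxima from the same data.
- **Information.** The split is by severe distortion, which is expected to be very rare. The 0–3 ratings from every subject are also collected, but neither section 4.2 nor section 4.3 relates them to misalignment.

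If both mattered, the study could end without saying whether distortion rises with misalignment, although the data for a fuller look were in hand.

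**Working it through.** **1. The plan's own figures.** No power or event count is stated for this table. The evaluable toric number reproduces: 169 × 0.9 = 152.1, given as 152. The primary comparison's stated power above 90% also reproduces. With 37 and 27 subjects at 1%, SE = √[0.01 × 0.99 × (1/37 + 1/27)] = 0.0252, and Φ(0.10/0.0252 − 1.645) = 0.99. Misalignment does not enter that comparison.

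**2. Expected severe toric subjects.** Protocol 20.6: "This assumes severe visual distortion rates of 1% for both the toric and control subjects". SAP section 7 assumes "severe visual distortion rates of 0.02 for toric and control subjects" and 200 toric subjects.

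| Inputs | Expected | P(none) | P(at most one) |
|---|---|---|---|
| 152 at 1% | 1.52 | 0.99^152 = 0.22 | 0.22 + 152 × 0.01 × 0.99^151 = 0.55 |
| 200 at 2% | 4.0 | 0.98^200 = 0.02 | 0.02 + 200 × 0.02 × 0.98^199 = 0.09 |

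On the current protocol's inputs, the severe column is therefore more likely than not to have no SD.

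**3. What the table can show.** With k severe subjects among N, the 95% half-width for the difference in means, in SD units, is 1.96 × √[1/k + 1/(N − k)]. The difference detectable with 80% power is 2.80 times the same root. For N = 152:

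| Severe subjects | Half-width (SD) | Detectable (SD) |
|---|---|---|
| 1 | 1.97 | 2.8 |
| 2 | 1.40 | 2.0 |
| 4 | 0.99 | 1.4 |

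The table can show only very large differences.

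**4. Angle.** The documents give no misalignment SD, so 4 to 8 degrees per eye is an assumption. The mean absolute angle is 0.798 × SD: 3.2, 4.8 and 6.4 degrees for SD 4, 6 and 8. Suppose raw 0–180 readings were subtracted without folding and meridians were uniform. The share of eyes wrapping is the mean angle divided by 180, so 3.2/180 = 1.8% to 6.4/180 = 3.5%. At SD 6 the mean would move from 4.8 to 9.2 and the SD from 3.6 to 27.2. That error requires printing, for example, 176 degrees for a marker at 2 and a meridian at 178. Protocol 7.1 describes two sets of marks 180 degrees apart that indicate a meridian, and the table's own maximum would expose such a value. The more realistic choice is signed or absolute: at SD 6, a mean near 0 or 4.8.

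**5. Eye.** For two independent eyes, the worse-eye mean is 1.128 × SD: 4.5, 6.8 and 9.0 degrees, against 3.2, 4.8 and 6.4 per eye. The printed level shifts by a factor of about 1.41, but whichever rule is used applies to both columns.

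**6. Visit.** For subjects with a 6-month answer, axis and keratometry are scheduled at the same visit. The gap concerns answers carried forward: at the planned drop-out, at most 169 − 152 = 17 toric subjects. Of these, only those with an earlier postoperative questionnaire count, and before 6 months it is given only after a spontaneous complaint or before a repositioning. If SAP 2.1 is read to cover repositioned subjects who attend at 6 months, those are added. Section 11.5 schedules an axis reading on the same occasions, so a same-visit pair should exist.

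**7. The graded alternative.** These are simulations on assumed inputs: n = 152, 1% severe, per-eye SD 6, 5–30% giving any rating.

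| Odds ratio per 5 degrees | Misalignment drives | Power, Spearman on 0–3 rating | Power, severe vs not |
|---|---|---|---|
| 2 | all grades (proportional odds) | 29–79% | 9–11% |
| 2 | severe ratings only | 5–6% | 9% |
| 1.5 | all grades (proportional odds) | 13–38% | 5–6% |
| 1.5 | severe ratings only | 5–6% | 6% |

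Ties also cap the correlation. With a share p giving any rating, the ceiling is roughly √[3p(1 − p)]: 0.38, 0.52 and 0.79 at 5, 10 and 30%, or about 0.39, 0.52 and 0.81 with the four grades. The 95% half-width at n = 152 is tanh(1.96/√149) = 0.16. At the low end, that interval sits on a scale ending near 0.39.

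**The case for a change.** The best case for a change is that the definitional gaps are real and closing them costs a line or two. Repositioned subjects are the cases where misalignment matters most, and a pre-procedure complaint paired with a post-procedure axis would mislead. The protocol synopsis also promises to set misalignment against reports of distortion generally, not only severe ones, so a graded analysis could be said to honour that promise.

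The gaps stand on the text. They are missing detail, though, and do not steer an analyst wrong. SAP 4.2 ties the measure to distortion at one postoperative time, and Protocol 11.6 has the axis read before a repositioning precisely to study distortion from misalignment. Same-visit pairing is the natural reading.

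The eye rule has no single right answer. The questionnaire asks how the subject sees with both eyes in general, so a worse-eye value, a two-eye mean or separate eyes are all defensible.

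The synopsis line names no method. The power gain for the graded analysis depends on an assumption that the documents cannot support. Mild and moderate ratings can also have other causes, since one of the five items covers headache and nausea. The analysis would be introduced after the interim look recorded in the Protocol Change History, and a null result could be taken as reassurance about severe cases that it does not give.

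**Conclusion.** No change is called for. The event counts are right: about 1.5 severe toric subjects on protocol 3.0 inputs and 4 on the 2015 SAP inputs. With them the table can show only differences of roughly 1.4 to 2.8 SD. That limits what the table can tell, but it does not make it a wrong analysis. It claims no test and no power. With the case detail in SAP 4.4 and the 1-year report in SAP section 6, it serves mainly to describe the severe cases.

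The open points on sign and folding, eye and visit are ordinary programming detail that an analyst would settle sensibly. None touches the primary endpoint. The graded correlation is a matter of preference: helpful under proportional odds, no gain if misalignment drives only severe ratings.

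The event counts rest on the planning rates of 1% and 2%. The angle, eye and power figures rest on an assumed spread of 4 to 8 degrees and on assumed odds ratios and rating frequencies, none of which the documents give.
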